2.4 Necrotising Enterocolitis of Grade II or Higher at 36 Weeks Corrected Gestational

Age

The endpoint 'Proven episode of stage II NEC Higher at 36 Weeks Corrected Gestational Age' will be derived using items from the "36 Weeks (OUTCOMES)" eCRF. The table below indicates how the eCRF items (shown in columns A and B) will be used to determine NEC status (column C).

5 6

1

3

4

(A) Did the baby have a proven episode of necrotising enterocolitis [itmNEC]		(B) Please specify stage of disease [itmNECSTAGE]	(C) Proven episode of stage II or III NEC	
No		- 0	No	
Yes	AND	Stage I	No	
Yes	AND	Stage II or III	Yes	

7

8

2.5 Late Onset Sepsis at 36 Weeks Corrected Gestational Age

The endpoint 'Late onset sepsis (LOS) at 36 Weeks Corrected Gestational Age ' will be derived using items from the "36 Weeks (OUTCOMES)" eCRF. The table below indicates how the eCRF items (shown in columns A and B) will be used to LOS status (column C).

11 12

10

(A) Did the baby have one or more episodes of infection proven [itmSEPSISYN]		(B) Date sample taken [itmSAMPDATE]	(C) LOS
No		-	No
Yes	AND	No more than 7 days beyond the week 36 target	Yes
Yes	AND	More than 7 days beyond the week 36 target	No

13

14

17

2.6 Treatment for Retinopathy (to Discharge)

- 15 The endpoint 'Treatment for Retinopathy to Discharge' will be directly derived from the item 'Was
- the baby treated for ROP?' [itmROPTREATYN]) on the "Discharge (DISCHARGE)" eCRF.

2.7 Time to Full Enteral Feeds

- 18 Time to full enteral feeds is measured from the date of randomisation to the date recorded in the
- eCRF corresponding to the 3^{rd} day on which enteral intake of ≥ 120 ml/kg/day was first achieved for
- 20 3 consecutive days.

2.8 Number of Blood Transfusions to 36 Weeks Corrected Gestational Age

- The number of transfusions to 36 weeks corrected gestational age is assessed by the question below appearing in the "36 Weeks (OUTCOMES)" eCRF:
 - How many transfusions of whole blood or packed cells? [itmNUMTRAN]

242526

21

22

23

- The number of transfusions will be set to 0 if the following item is answered 'No':

 Did the baby have a transfusion before 36 weeks? [itmTRANYN]
- 27

28

2.9 Chronic Lung Disease at 36 Weeks Corrected Gestational Age

The endpoint 'Chronic lung disease at 36 Weeks Corrected Gestational Age ' will be derived using items from the "36 Weeks (OUTCOMES)" eCRF. The table below indicates how the eCRF items (shown in columns A to C) will be used to derive chronic lung disease status (column D).

(A) Did the baby receive respiratory support at any time? [itmVENT]	(B) Is the baby still on supplemental oxygen at 36 weeks? [itmVENT36WKS]	(C) "Date last on supplemental oxygen or on assisted ventilation" [itmVENTDATE]		_ (D) Chronic lung disease	
No				No	
-	No			No	
7 -	Yes	AND	No more than 7 days before week 36 target	Yes	
	Yes	AND	More than 7 days before week 36 target	No	

2.10 Length of Hospital Stay

- 7 Hospital length of stay is measured from the date of birth to the date the baby is discharged from
- 8 hospital.

2.11 Survival and Development Outcomes at 24 to 36 Months Corrected Gestational Age

Major disability is defined as meeting any of the criteria below based on an evaluation performed during the assessment window using the instruments below;

- a modified Short Health Status Questionnaire (SHSQ) completed by a medically qualified practitioner documenting:
- a) major developmental delay, including language or speech problems, or
- b) cerebral palsy with inability to walk unassisted, or
- c) severe visual loss (cannot fixate/ legally blind, or corrected acuity <6/60 in both eyes), or
- d) deafness, requiring a hearing aid or cochlear implants.
- A cognitive composite score from the Bayley-III Scales of Infant and Toddler Development (BSID) indicative of least moderate delay (i.e. a score at least 2 SDs below the age-adjusted norm on the index)
- A problem solving score from the Ages and Stages Questionnaire (ASQ) indicative of least
 moderate delay (i.e. a score at least 2 SDs below the age-adjusted norm on the index. Note
 that a LIFT substudy will, blinded to treatment, compare available BSID data with
 corresponding ASQ data to ensure the chosen ASQ score cut-point corresponds adequately
 well to that for the BSID).

Survival status is collected at discharge and annually thereafter. An infant will be classified as being alive and free from major disability if none of the criteria above are met and adequately complete information is obtained during the assessment window from at least one of the instruments. Any unclear cases (e.g. where only partial information is available, a death occurs after the date of the developmental assessment and before month 36, etc.) will be resolved on blinded clinical review of available information.

1 2.12 Safety

5

6

7

8

9

10

11

12

13

16

23

27

34

- 2 In addition to the morbidity endpoints defined above, safety will be assessed according to the
- 3 incidence of suspected adverse reactions that are classified as serious and unexpected (Suspected
- 4 Unexpected Serious Adverse Reactions SUSARs).

3 Analysis Sets

- The ITT population will comprise all randomised participants.
- The Per Protocol population will comprise all randomised participants that receive least one administration of their assigned treatment and who are not deemed ineligible on blinded clinical review.
- The safety population will comprise all randomised participants who received at least one administration of assigned treatment. Participants will be analysed according to the treatment they actually received for the purposes of the safety analysis.

Any instances where membership of an analysis set is unclear will be resolved on blinded clinical review. Any exclusions from analysis sets will be documented.

4 Interim and Final Analyses

- 17 The LIFT protocol makes provision for interim analysis of the primary composite endpoint, and of
- survival to discharge, using the Haybittle–Peto approach (see Peto et al¹, Statistical Note No. 4, p.
- 19 611). The procedure involves evaluating the test statistic calculated under null hypothesis against a
- boundary of 3 standard deviations (equivalent to $\chi_1^2 = 9$, with p-value of 0.0027). This has a
- 21 negligible effect on the alpha level applicable at final analysis (i.e. the analysis performed when the
- boundary is not crossed at any interim analysis and the study continues as originally planned).

5 Type I Error (Alpha)

- 24 A two-sided alpha (significance level) of 5% will be applied to the analysis of the primary composite
- 25 endpoint. There will be no adjustment to alpha for interim analyses evaluated using the Haybittle-
- 26 Peto boundary.
- 28 The key secondary endpoints for LIFT comprise the individual components of the primary composite
- 29 endpoint (i.e. survival, brain injury, NEC, LOS, and RoP). P-values adjusted for the five comparisons
- 30 performed for this set of endpoints will be derived using Benjamini-Hochberg procedure² with a
- 31 family-wise error rate of 5%. Results of other endpoint, subgroup, and sensitivity analyses will be
- 32 interpreted in proper context and with due consideration of type I error. The clinical interpretation
- of the statistical evidence from LIFT will take into account the recommendations of Pocock et al^{3,4}.

6 Analysis of Study Endpoints and Patient Characteristics

- 35 Safety analyses will be performed using the safety population. Non-safety analyses will be
- 36 performed using the ITT population. Sensitivity analyses may be performed using the Per Protocol
- 37 population.

1 6.1 Subject Disposition

2 The number of patients in each analysis set will be presented along with reasons for any exclusions.

3 6.2 Baseline Demographic and Clinical Characteristics

- 4 Descriptive statistics will be prepared to summarise the baseline characteristics of the study
- 5 participants by treatment allocation. Variables to be summarised include: gender, multiple birth,
- 6 birth weight, gestational age at birth, inborn/outborn, mode of delivery, and APGAR scores at 1 and
- 7 5 minutes.

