6.5 Analysis of Categorical Secondary Endpoints

- 26 Secondary categorical endpoints include: survival to hospital discharge (Section 2.2), brain injury
- 27 (Section 2.3), NEC (Section 2.4), LOS (Section 2.5), RoP (Section 2.6), chronic lung disease (Section
- 28 2.9), and survival and development status at 24-36 months corrected gestational age (Section 2.11).

29

- 30 Secondary categorical endpoints will be analysed using the same modelling approach applied to the
- 31 primary endpoint (i.e. a log-binomial model fitted using generalised estimating equations to
- 32 accommodate possible correlation of data between siblings from multiple births. If the log-binomial
- 33 model does not converge, a logistic model will be used).

- 35 Sensitivity analyses will be undertaken on the categorical morbidity endpoints (i.e. brain injury, NEC,
- 36 LOS, RoP, and chronic lung disease) in which any missing values due to death are treated as an
- 37 event. An analysis of survival to 36 weeks may also be undertaken as a sensitivity analysis. Estimates
- 38 of the treatment effect on survival to hospital discharge that are adjusted for adherence will be
- 39 produced using the methods detailed in Section 8.2 in a sensitivity analysis.

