6.7 Safety Data Analysis

A descriptive analysis of SUSAR data will be conducted by treatment allocation. The event rate is expected to be low, and thus an exact test would be an appropriate choice to perform any formal comparisons between the two groups in the proportion experiencing a SUSAR.

7 Subgroup Analyses

Consistency of the treatment effect on the primary endpoint across subgroups will be tested by including a treatment-by-subgroup interaction term (along with the relevant main effect terms) as covariates in the analysis model (as specified in Section 6.4).

The subgroups of interest are: (i) birthweight <1000 g versus 1000-1499 g; (ii) randomised ≤72 hr versus >72 hr from birth; (iii) those who received versus did not receive probiotics by 36 weeks corrected gestation (note: this is a post-baseline covariate); (iv) ≤ 28 weeks versus >28 weeks gestation at birth. Because 'probiotic use by week 36' is a post-baseline covariate, an unbiased evaluation of its role as an effect-modifier will be attempted by categorising participating sites (NICUs) into tertile subgroups according to their propensity to use probiotics, and evaluating consistency of the treatment effect across these sub-groups.

Adjusted Analyses

8.1 **Stratification Factors**

Sensitivity of results obtained from the primary analysis of the primary endpoint to adjustment for stratification factors will be explored by included them as covariates in the model (See Section 6.4).

4 5 6

7

8

9

10

11

14

15

16

1

2

3

- Randomisation is stratified by gender, birth weight (<1000 g vs ≥1000-1499 g), according to whether the baby is from a single or multiple birth, and site (NICU). Given the modest number of patients at some sites, and the degree of variation in the number of babies recruited across sites (i.e. minimum is less than 10 babies and the maximum is more than 200 babies), sites will be categorised into larger groups that have a comparable pooled primary endpoint event rate. This will be done by estimating, in a blinded fashion, the event risk at each site pooled across treatments, and deriving 'risk classification' according to tertiles. Risk classification will be used as the covariate in the
- 12

13 adjusted analyses in preference to 'individual site'.

8.2 **Treatment Compliance**

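### Apart from the endpoints compared by arm, the safety analysis counts only SUSARs, so a serious suspected reaction classed as expected would enter no planned safety table; the number affected is unknown and may be zero.

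*SAP*

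**What the plan says.** Section 2.12 has two parts. The first brings the trial's morbidity endpoints into the safety assessment: "In addition to the morbidity endpoints defined above, safety will be assessed according to the", and the second follows directly as the "incidence of suspected adverse reactions that are classified as serious and unexpected". The SAP labels these events SUSARs.

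Section 6.7 plans the analysis of the second part and of nothing else: "A descriptive analysis of SUSAR data will be conducted by treatment allocation". It expects few such events and says "thus an exact test would be an appropriate choice" for any "formal comparisons between the two groups in the proportion experiencing a SUSAR". The plan is therefore mainly descriptive, and the formal test is optional.

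Section 3 defines the safety population as babies who received at least one administration of assigned treatment. It adds: "Participants will be analysed according to the treatment they actually received for the purposes of the safety analysis". The opening of Section 6 assigns safety analyses to that population. Neither place adds a further safety outcome.

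**The concern.** A SUSAR must meet three conditions: suspected, serious and unexpected. The first two describe the event and its possible link to the supplement. The third describes what was already known about the product. Expectedness is useful for deciding which single cases need expedited reporting, but it does not bear on whether an event is more frequent in one arm than in the other.

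Used as the entry condition for a comparison by arm, expectedness leaves out a serious suspected reaction because it is already recognised. If such reactions occurred more often on bLF and fell outside the trial's endpoints, no table planned in the SAP would show it. A low and balanced SUSAR count would then describe only part of the serious suspected reactions reported.

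**Working it through.** No arithmetic applies. The SAP gives no SUSAR rate, no rate of expected reactions, and no size or power for the safety comparison. The check is a reading of every place where the SAP fixes a safety outcome or compares a serious event by arm.

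**Step 1. Where safety outcomes are fixed.**

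| SAP section | What it contributes | Covers serious suspected reactions classed as expected? |
|---|---|---|
| 2.12 | Morbidity endpoints plus SUSAR incidence | Only if the event is also one of the endpoints |
| 3 | Safety population, analysed as treated | Adds no outcome |
| 6, opening | Assigns safety analyses to the safety population | Adds no outcome |
| 6.7 | Descriptive SUSAR analysis, with an exact test on the SUSAR proportion if a test is done | No |

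No section tabulates all serious suspected reactions, all serious adverse events, or expected serious reactions.

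**Step 2. Which serious events are compared by arm in any case.** Section 6.5 lists survival to discharge, brain injury, NEC, late onset sepsis, treated retinopathy, chronic lung disease, and survival and development status at 24 to 36 months. It also plans a further look at the morbidities: "Sensitivity analyses will be undertaken on the categorical morbidity endpoints (i.e. brain injury, NEC" and the remaining ones, with values missing because of death counted as events. Section 6.6 compares transfusions, time to full enteral feeds and length of stay. None of these depends on a judgement of causality or expectedness.

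They are, however, fixed definitions. Section 2.4, for example, sets stage I NEC to No, and Section 2.5 sets late onset sepsis to No when the sample was taken more than 7 days beyond the week 36 target.

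**Step 3. Sort every serious suspected reaction by these rules.**

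- Unexpected: counted as a SUSAR under 2.12 and 6.7.
- Expected, and meeting an endpoint definition: not a SUSAR, but counted in that endpoint's comparison.
- Expected, and meeting no endpoint definition: counted nowhere in the planned safety analysis.

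In reactions: all serious suspected = SUSARs + expected. The group left out is the expected reactions minus those captured by an endpoint.

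In babies, which is the unit of the proportion in 6.7, a wider row would add only babies who had an expected serious suspected reaction and no SUSAR.

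**Step 4. Size.** The lower limit of the group left out is zero, reached if no serious reaction to bLF is classed as expected. The SAP gives no figure from which an upper limit could be derived.

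**The case against.** The strongest reply is that the gap may be empty. The SAP names no recognised serious reaction to bLF and mentions no reference safety information. If nothing serious is classed as expected, SUSARs and serious suspected reactions are the same set and nothing is lost. This stands, and it is why the point is minor.

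A second reply is that coverage is broad. In babies under 1500 g, many serious harms of an enteral supplement would plausibly register as death, NEC, sepsis or another endpoint, without relying on an investigator's attribution. This also stands in large part. It does not close the gap, because 2.12 itself adds a reaction-based measure to the endpoints, and that added measure is the one filtered by expectedness.

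A third reply is that collection of adverse events and the judgement of expectedness belong to the protocol, which is not at hand. That is fair for collection and definitions. The choice of what is analysed is nevertheless stated in the SAP, so the point concerns a rule the SAP sets and not a detail it leaves out.

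A reader might go further in three ways that the document does not support:

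- That the rule removes the reactions most plausibly caused by bLF. Suspicion of causality is already required for a SUSAR, and nothing in the SAP ranks expected reactions as more likely to be causal.
- That a reaction could be counted early and dropped later after an update of the reference information. No section mentions such information or an update to it.
- That the trial would declare the arms equally safe on the SUSAR count alone. The SAP plans no such conclusion, and the endpoint comparisons would be reported beside it.

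**Conclusion.** The point holds as a gap in definition. Beyond the endpoints compared by arm, Sections 2.12 and 6.7 limit the reaction-based safety analysis to SUSARs, so a serious suspected reaction that is classed as expected and is not captured by an endpoint enters no planned safety table.

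Its size is unknown and may be zero, and no actual event is shown to have been lost. The conclusion assumes that the SAP's wording is the full statement of the planned safety analysis. The practical effect also depends on whether any serious reaction to bLF is classed as expected, which this document does not say. The point is a minor, inexpensive improvement. It does not affect the primary analysis.

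**What to change.** In Sections 2.12 and 6.7, define the reaction-based safety outcome as the proportion of babies with any serious suspected adverse reaction, expected or not. Tabulate it by arm, with SUSARs as a sub-row, and use the same exact test for any formal comparison. If no serious reaction is classed as expected, the two rows will be identical and the table will show that.

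The cost in text is about one sentence in 2.12, matching wording in 6.7, and one table row. Each SUSAR must first have been judged serious and suspected, so the wider set of reports should already have been assessed. The SAP does not show whether the reports classed as expected are held in the trial database by arm, and this should be confirmed. The downside is minor reconciliation of reports that were not expedited.

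A separate matter can be settled in the same edit: 6.7 presents SUSARs by allocation, while Section 3 analyses safety by treatment received. The two should be reconciled.

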9.2 LIFT_Canada

- 14 The protocol for the Australia and New Zealand (ANZ) LIFT trial was used to develop a similar
- 15 Canadian trial (LIFT_Canada: ClinicalTrials.gov identifier NCT03367013) with a sample size target of
- 16 N=500. Individual patient data from LIFT Canada is planned to be combined with that from LIFT (the
- 17 studies use identical electronic Case Report Forms) in order to perform pooled analyses. The pooled
- analyses will follow the methods described in this document with the following modifications: (1)
- 19 the method for aggregating sites (NICUs) described in Section 8.1 will be implemented separately for
- 20 ANZ and Canada; and, (2) evidence of heterogeneity of treatment effect across region (i.e. ANZ
- 21 versus Canada) will be evaluated on the primary endpoint.
- 22

- 23 The timing of this pooled analysis will depend on when LIFT-Canada data becomes available. This is
- 24 expected in late 2020, about 2 years after the release of LIFT Australia and New Zealand results,
- 25 based on current projections. The pooled results will be included in a further update of the Cochrane
- 26 review of enteral lactoferrin supplementation in preterm infants.

10 References:

- 2. Huque M. F. Validity of the Hochberg procedure revisited for clinical trial applications. Stat Med 2016;35:5-20.
- 3. Pocock S. J., Stone G. W. The Primary Outcome Is Positive Is That Good Enough? New Engl J Med 2016;375:971-9.
- 4. Pocock S. J., Stone G. W. The Primary Outcome Fails What Next? New Engl J Med 2016;375:861-70.

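### SAP Section 5 names Benjamini-Hochberg, claims a 5% family-wise error rate and cites a paper on the Hochberg procedure: the three do not agree, and the 5% is not guaranteed when two to four of the five nulls are true

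*SAP*

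**What the plan says.** SAP Section 5 (Type I Error) makes the components of the primary composite the key secondary family: "endpoint (i.e. survival, brain injury, NEC, LOS, and RoP". It promises "P-values adjusted for the five comparisons", and these comparisons, "performed for this set of endpoints will be derived using Benjamini-Hochberg procedure", are tied to a "family-wise error rate of 5" per cent. The superscript on the method points to reference 2 in Section 10, whose title is "Validity of the Hochberg procedure revisited for clinical trial applications".

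The SAP does not mention the false discovery rate. It also has no gatekeeping or other rule that would turn Benjamini-Hochberg into a family-wise procedure. This is the only multiplicity adjustment that Section 5 specifies for secondary endpoints.

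**The concern.** The sentence fixes a method, an error rate and a source, and they point in different directions. Benjamini-Hochberg and Hochberg are both step-up tests with similar names, but they use different thresholds and control different quantities. Benjamini-Hochberg limits the expected share of false claims among the claims made. Hochberg limits the chance of any false claim at all.

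Two things are at stake. First, if some components respond to lactoferrin and others do not, the chance of a false claim on a non-responding component may exceed the 5% the plan states. Second, the statistician who implements the sentence must decide which part of it to follow. If that is settled after the p-values are known, the plan has left open a choice it was meant to close.

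**Working it through.** **Inputs.** From SAP Section 5: five comparisons and a 5% error rate for the family. Two-sided tests are assumed for the components; the SAP states this only for the primary ("A two-sided alpha (significance level) of 5% will be applied to the analysis of the primary composite" endpoint). Component effect sizes and correlations are not in the SAP, so they are assumed and varied.

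**Thresholds for the ordered p-values, i = 1 to 5.**
- Benjamini-Hochberg, i × 0.05/5: 0.01, 0.02, 0.03, 0.04, 0.05.
- Hochberg, 0.05/(5 − i + 1): 0.01, 0.0125, 0.0167, 0.025, 0.05.

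Each rule finds the largest i whose ordered p-value meets its threshold and rejects that hypothesis and all those with smaller p-values.

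**Where the stated 5% is reproduced (Benjamini-Hochberg).**
- All five nulls true, independent tests: family-wise error 5.0%. Here any rejection is false, so the false discovery rate and the family-wise error coincide.
- One true null: its p-value is never compared with more than 5 × 0.05/5 = 0.05, so the error cannot exceed 5%.

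**Where it is not reproduced: closed form, independent tests, near-certain real effects.** The real effects take the first places, and the nulls face the remaining thresholds.
- Three real effects, two nulls (thresholds 0.04 and 0.05): no false rejection requires both null p-values above 0.04 and not both at or below 0.05. Error = 1 − (0.96² − 0.01²) = 7.85%.
- Two real effects, three nulls (thresholds 0.03, 0.04, 0.05): start with all three above 0.03, 0.97³ = 0.912673. Subtract two or more in 0.03–0.04, 3 × 0.01² × 0.96 + 0.01³ = 0.000289. Subtract none or one there with the rest in 0.04–0.05, 4 × 0.01³ = 0.000004. Error = 1 − 0.912380 = 8.76%.

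**Range over assumed power.** Both rules depend only on which interval between thresholds each p-value falls in, so under independence the error can be summed over all 6⁵ = 7,776 combinations. A null p-value is uniform. For a real effect, P(p ≤ t) = Φ(δ − z) + Φ(−δ − z), with z the two-sided critical value for t. The shifts δ = 1.43, 1.96, 2.80, 3.24 and 10 give 30%, 50%, 80%, 90% and near-certain power at an unadjusted 5%.

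Family-wise error (%), by number of real effects among the five; the last column is the largest Hochberg value in the row:

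| Power per real effect | 0 | 1 | 2 | 3 | 4 | Hochberg, largest |
|---|---|---|---|---|---|---|
| 30% | 5.0 | 4.7 | 4.2 | 3.2 | 1.9 | 4.9 |
| 50% | 5.0 | 5.4 | 5.2 | 4.4 | 2.7 | 4.9 |
| 80% | 5.0 | 6.6 | 7.2 | 6.4 | 4.1 | 4.9 |
| 90% | 5.0 | 7.1 | 7.9 | 7.1 | 4.6 | 4.9 |
| Near-certain | 5.0 | 7.8 | 8.8 | 7.9 | 5.0 | 5.0 |

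Simulation with 1,000,000 replicates per scenario agrees to about 0.1 percentage point. With a common correlation of 0.3 the maxima at 50%, 80%, 90% and near-certain power are 5.3%, 6.7%, 7.4% and 8.4%. With correlation 0.6 the overall maximum is 7.4%. Without adjustment and with all nulls true, the error would be 1 − 0.95⁵ = 22.6%.

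**What Benjamini-Hochberg does hold.** With 0 to 4 near-certain real effects and independent tests, the false discovery rate is 5%, 4%, 3%, 2% and 1%.

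**Effect on conclusions.** Take illustrative raw p-values 0.009, 0.018, 0.028, 0.20, 0.60.
- Benjamini-Hochberg (multiply by 5/i, then take the minimum from i upwards): 0.045, 0.045, 0.047, 0.25, 0.60. Three components are significant.
- Hochberg (multiply by 5 − i + 1, then the same minimum): 0.045, 0.072, 0.084, 0.40, 0.60. One component is significant.

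**The case against.** The strongest reply is that little harm follows. The family is fixed in advance, and Benjamini-Hochberg does give 5% when lactoferrin affects none of the components. Single components are rarer than the composite, so high power for several of them is a strong assumption; at about 30% power there is no excess, and at 50% it is under half a percentage point. Even the worst case, 8.8%, is far below 22.6%. If raw p-values are reported, a reader can apply either adjustment. All of this stands. It limits the size of the problem, but it does not make the sentence consistent or tell the analyst which rule to apply.

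A reader might infer more than the document supports:
- That Benjamini-Hochberg holds 5% only when all five nulls are true. It also does so when exactly one null remains.
- That the family-wise error in this trial will be near 9%. That needs two near-certain real effects, and the SAP gives no component power from which to claim it.
- That the authors meant Hochberg and mistyped the name. The reference title points that way, but the wrong element could equally be the phrase about family-wise error.

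**Conclusion.** The point holds as an inconsistency in Section 5: the named method does not deliver the stated error property, and the citation concerns a different method. What is missing is a guarantee of 5% when two to four of the five nulls are true.

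For independent two-sided tests with equal power on each real effect, the maximum runs from no excess at about 30% power to 8.8% with near-certain effects. Moderate positive correlation lowers the upper end slightly. Effect sizes and correlations are assumptions throughout.

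The primary endpoint's two-sided 5% alpha is untouched. The matter should be corrected before unblinding because it can change which components are declared significant, but it does not threaten the trial's main conclusion.

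**What to change.** Before unblinding, amend the sentence in SAP Section 5 in one of two ways. They are of equal standing, and the trial statistician should choose according to which error rate is intended.

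- **(a) Family-wise control.** Name the Hochberg procedure and keep the 5% family-wise error rate. This agrees with the title of reference 2. The guarantee rests on independent or positively dependent tests, which is plausible for these components.
- **(b) False discovery rate control.** Keep Benjamini-Hochberg, state a 5% false discovery rate in place of the family-wise claim, and replace the citation with one for that procedure.

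The drafting cost is a few words. Under (a) the adjusted p-values are equal or larger and a component can lose significance, as in the example where three significant results become one. Under (b) the report can no longer claim family-wise control for the components.
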